9.6 Data Management

Data management is maintained at each registry according to their internal processes. Only final analysis tables (i.e., no patient-level data) will be provided to the marketing authorisation holder.

9.6.1 Data Management for Cystic Fibrosis Trust Patient Registry

Within the CF Trust Patient Registry, there are inbuilt verification tools that will "flag-up" any abnormal values that are out of the normal ranges directly to the sites and, in some instances, to the Registry Team. Throughout the year, regular (monthly) data verification is carried out by the Registry Team, running programmes looking at unusual data entries (e.g., abnormal height and weight). Any queries are then reported back to the sites for verification. Any duplicate registration of patients is also checked on a monthly basis, and if found, records are merged with no loss of data, thus maintaining a "clean" data set of patients.

Following the annual data cut, extensive data cleaning is undertaken in conjunction with the Bio-Statisticians at Imperial College London.

Data completeness is assessed each year. For patients known to be alive, 89% have evidence of at least an annual encounter in the CF Trust Patient Registry database. For patients with at least an annual encounter visit, 95% have evidence of pulmonary function measure (e.g., FEV₁).

9.6.2 Data Management for Cystic Fibrosis Foundation Patient Registry

CF Foundation imports data from the registry back-end database to the registry server and has processes in place for verifying the data format, modifying data, and removing duplicate records. As a rule, the CF Foundation attempts to do as little corrections to the raw data as possible. Only authorised CF Foundation employees have access to the database. Details of the data management processes at the CF Foundation are provided in [Stand-alone Document 3](#) (listed in Annex 1. List of Stand-alone Documents).

Data completeness in the CF Foundation Patient Registry is stimulated by tying up the amount of annual grant awards to the CF centres to the quality of data entered to the registry. As a result, 94% of patients' records in 2011 had medications data, 91% had complications data, and 91% had microbiology data. In addition, 96% of CF nontransplant patients 6 years or older and known to be alive had recorded pulmonary function test measurements.

9.7 Data Analysis

Some data analysis methods are provided in Section 9.3. A detailed analysis plan will be presented in a statistical analysis plan.

9.8 Quality Control

9.8.1 Quality Control for Cystic Fibrosis Trust Patient Registry

The UK CF Trust registry has regular quality testing by the hosting company with respect to the encryption and safety of the data held. The application is held in Amsterdam in accordance with EU recommendations. There are elaborate encryption protocols in the production of user access including a unique person-specific username and unique password. The password has to be changed every 30 days. The data can only be seen by the user site, and data cannot be moved between sites without the Registry Team being involved. The registry is in the process of receiving the Short Leap Shared Protection Certificate and has the Secure Site Pro Secure Sockets Layer Certificate required for large databases.

The registry is operated by the CF Trust in a password-protected, locked office in accordance with the ethical requirements for approval of the registry. The Registry Team are "*trusted third parties*" and conform to the Data Protection Act in full.

Centres and clinics are monitored on a regular basis by the Registry Team. Study monitoring visits are scheduled with the sites on a regular basis to ensure that data are recorded in the patient notes as well as on the registry, in accordance with usual practice. All entries are checked to ensure accuracy. Any discrepancies are documented and verified with the sites. Visit logs will be kept up to date. Random sets of patients' notes are also checked at the visits to ensure no bias in the registry data.

During this study, the Registry Team conduct regular monthly data verification. A Registry Helpdesk is available to respond within 24 hours to queries; all sites are encouraged to use this Helpdesk. The Registry Team is also available by e-mail and telephone.

9.8.2 Quality Control for Cystic Fibrosis Foundation Patient Registry

The responsibility for the quality of the CF Foundation registry data lies with the CF centres. The annual grants application signed by all centre directors has a clause that states that the

registry data provided by the centre is accurate to the best of the centre's director knowledge. Some of the key data entries (e.g., death dates) are verified with the centres' data entry staff after the end of the reporting year. There are also documented evidences about almost-perfect match between the registry data and the data from the clinical studies that involve patients with CF. Understanding an importance of additional assurances in the quality of the registry data, CF Foundation will be conducting an audit of 5% of the registry records annually.

9.9 Limitations of the Research Methods

Limitations of missing data

Missing data may introduce misclassification of exposure and outcomes in observational studies. The CF Trust and CF Foundation patient registries have robust systems in place to minimise missing data in their patient registry databases. These procedures are described in the data management and quality control sections (Sections 9.6 and 9.8). For the CF Trust, data completeness is assessed each year. Of patients known to be alive, 89% have evidence of at least an annual encounter in the CF Trust Patient Registry database. Amongst patients with at least an annual encounter visit, 95% have evidence of pulmonary function measure (e.g., FEV₁). For the CF Foundation, data completeness in the CF Foundation Patient Registry is stimulated by associating the amount of annual grant awards to the CF centres to the quality of data entered. As a result, 94% of patients' records in 2011 had medications data, 91% had complications data, and 91% had microbiology data. Additionally, 96% of CF nontransplant patients 6 years or older and known to be alive had recorded pulmonary function test measurements. Whilst missing data are minimised in the patient registries, exploratory and sensitivity analyses will be employed to understand the impact of missing data on the primary objectives of the study.

Limitations of observational studies

The nature of observational studies with nonrandom treatment assignment allows for the concern of selection bias. The concern is that patients treated with ivacaftor could be systematically different and have different risk factors for adverse events than patients who choose other treatments or are not eligible for ivacaftor. The design strategy of this study is a matched-comparator cohort (patients who have not been exposed to ivacaftor). Selection bias will be minimised by matching on age group, *CFTR* genotype class, and sex, as appropriate. Other variables that may influence selection bias, such as pancreatic sufficiency status or diabetes status, will be assessed as confounders in the statistical analyses through stratification and adjustment, when possible.

Another limitation of the observational study design is differential follow-up of the patient cohorts, which can introduce ascertainment bias of outcomes. To minimise this bias, the CF patient registries collect comprehensive data at least annually on all patients enrolled. To identify whether ascertainment bias is introduced into the study, cohorts will be compared for healthcare utilisation including CF care visits and hospitalisations.

Additionally, because eligibility for a cohort is determined each year, a patient may be included in different cohorts over the course of this study. This would limit the ability to include this patient in longitudinal evaluations, such as for change in lung function over time.

Limitations of study setting

The analysis of CF disease progression will be limited to CF lung disease severity and clinical signs of CF disease progression, based on definitions accepted in the medical community. Although the change in lung function over time will be analysed, the analysis is limited by differences in the frequency of data collection for pulmonary function testing. Pulmonary function test results are collected in both the CF Trust and the CF Foundation patient registries. However, the CF Trust database collects pulmonary function test results at the annual encounter only, whilst the CF Foundation allows CF care providers to enter pulmonary function test results for all patient encounters throughout the year. In either case, data are collected only if available. Additionally, the CF Trust collects only the best pulmonary function test result (newly implemented in 2012), whereas the CF Foundation collects the actual result at each encounter.

Whilst the patient registries do not provide the precision of a clinical study where all patients have pulmonary function testing at a defined and frequent interval, the available pulmonary function test data will be used to define CF lung disease severity (see Section 9.3) and provides a qualitatively accurate measurement of CF disease progression amenable to annual reporting. Given the variability in the number of data points available for each patient, analysis of the change in lung function over time utilising registry data is likely underpowered to detect differences between the Ivacaftor and Comparator Cohorts.

Limitations of the use of a Historical Cohort

The use of a Historical Cohort may also introduce bias in several ways. Data from a Historical Cohort are, by definition, different from the Comparator Cohort (selected from the same period as the Ivacaftor Cohort) because the CF care (e.g., medications, nonpharmacologic therapies, and treatment guidelines) have changed over time. Additionally, because the majority of patients with the *G551D* mutation are likely to be currently receiving ivacaftor, the Historical Cohort is likely to comprise the same patients, but at a different disease state (e.g., higher lung function, fewer clinical signs, and symptoms). The data fields for the registries are also modified slightly over time, limiting the ability to directly compare data from the Historical Cohort with those of cohorts based on more recent time periods.

Limitations on power and sample size

The number of patients included in annual analyses will be dependent on the use of ivacaftor amongst patients in the registries. As of 2010, the enrollment of patients with the *G551D-CFTR* mutation is 432 in the CF Trust and 1035 in the CF Foundation.^{1,2} Therefore, the power to detect differences in the study endpoints is limited. Whilst we explored the study power for detecting differences in mortality, the study is powered to detect 2- to 3-fold differences between study cohorts. One method to increase power would be to combine data from individual patient registries. Combining data sources was previously considered by the leadership of the patient registries in the UK and US independent of this study protocol, and they advised that previous pooled analysis has been limited to matching at the encounter level and methods for combining annual data have not been established. Throughout the conduct of the study, the feasibility of combining annual registry data will be further explored.

Limitations on the analyses for prior hypotheses

Given the scientific interest in the assessments of pulmonary exacerbations and adverse events in the CF population, a null hypothesis would be that there is no difference in the incidence of these events between Ivacaftor and Comparator Cohorts or perhaps a lower incidence in the Ivacaftor Cohort. However, the analyses are limited by a number of factors. The lack of knowledge on the background risk of specific adverse events in the target CF population means that it is not possible to predict whether the number of patients in each registry will be sufficient to power the detection of statistically significant differences between the Ivacaftor and Comparator Cohorts. The small sample size may also lead to spurious results that may confound interpretation, and the manner in which pulmonary exacerbations are collected do not allow direct comparison to the incidence of pulmonary exacerbation observed in Phase 3.

For the specific prior hypothesis on pulmonary exacerbation, the CF Trust and CF Foundation registries do not predefine the clinical presentations that constitute a pulmonary exacerbation. Therefore, there is likely some variability in pulmonary exacerbation events within each registry and across both registries. Further, because the data sets are based on existing registry variables, adverse drug reactions, and adverse events in the SmPC will rely on mapping variables and/or rely on CF care centres providing text entries that are mappable.

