 1. Patients with CF in the CF Trust or the CF Foundation patient registries
 2. Patients with *G551D-CFTR* mutation
 3. Patients with no evidence of ivacaftor exposure before ivacaftor was available commercially
- Exclusion Criterion
 1. Participation in an interventional study during the analysis period (if available)

Ivacaftor Pregnancy Study Cohort

- Inclusion Criteria
 1. Female patients with CF in the CF Trust or the CF Foundation patient registries
 2. Patients 13 years of age or older
 3. Patients treated with ivacaftor
- Exclusion Criterion
 1. Participation in an interventional study during the analysis period (if available)

Comparator Pregnancy Study Cohort

- Inclusion Criteria
 1. Female patients with CF in the CF Trust or the CF Foundation patient registries
 2. Patients 13 years of age or older
 3. Patients with no evidence of ivacaftor exposure (current or past)
 4. Patients matched on *CFTR* genotype class to patients in the Ivacaftor Pregnancy Study Cohort
- Exclusion Criterion
 1. Participation in an interventional study during the analysis period (if available)

Drug Utilisation Cohort

- Inclusion Criteria
 1. Patients with CF in the CF Trust or the CF Foundation patient registries
 2. Patients with current evidence of ivacaftor exposure
- Exclusion Criterion
 1. Participation in an interventional study during the analysis period (if available)

Variables In both registries, all patients participate in standard encounter-based data collection including annual assessments for exposure, death, organ transplantation, hospitalisations, CF complications, pulmonary exacerbations and respiratory microbiology, pregnancy, and pulmonary function. (However, the CF Trust Patient Registry only includes annual data for each patient.) Investigators at CF care centres enter data for their enrolled patients with CF into the registry databases. To meet the study objectives, data for safety- and disease

progression-related outcomes will be analysed separately for each registry for 5 years.

Exposure

Ivacaftor exposure, as reported by CF physician to the patient registry

Endpoints

1. Safety:
 - Death
 - Organ transplant
 - Hospitalisations
 - CF complications including but not limited to hepatobiliary, gastrointestinal, and pulmonary conditions
 - Pulmonary exacerbations and respiratory microbiology
 - Serious safety outcomes
2. Pregnancy
 - Live birth
 - Stillbirth
 - Spontaneous abortion
 - Therapeutic abortion
 - Gestational age

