8.3 Prior Hypotheses

The purpose of this study is to perform analyses that will inform us on the long-term safety of ivacaftor use in patients with CF. Given the known safety profile of ivacaftor, this study will further characterise the safety of chronic ivacaftor treatment in real-life use and provide descriptive analyses on specified safety and CF disease progression outcomes using observational data. These analyses will be used for hypothesis generation for safety issues that warrant future study. Therefore, no prior hypotheses are proposed for the primary objectives. Prior hypothesis is provided for specific secondary objectives, although the study may be underpowered to detect any differences:

- Pulmonary exacerbations: similar or lower incidence in the Ivacaftor Cohort than the Comparator Cohort and previously observed in the pivotal Phase 3 studies (as described in the Summary of Product Characteristics [SmPC])
- Adverse drug reactions (as listed in the SmPC): similar or lower incidence in the Ivacaftor Cohort than the Comparator Cohort and previously observed in the pivotal Phase 3 studies (as described in the SmPC)
- Serious adverse events and adverse events leading to withdrawal of ivacaftor: similar or lower incidence in the Ivacaftor Cohort than the Comparator Cohort (CF Trust data only).

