9.3.1.2 Outcomes

Death will be defined if there is evidence of a date of death in the database. Cause of death will include respiratory/cardiorespiratory, liver disease, trauma, suicide, transplant-related, and other.

Organ transplantations will be defined if there is evidence of an organ transplantation. Type of transplant will include lung and other.

Hospitalisations will be defined if there is evidence of a start date for a hospitalisation for a pulmonary exacerbation.

CF complications include the following:

- allergic bronchial pulmonary aspergillosis (ABPA)
- absence of vas deferens
- arthritis
- arthropathy
- asthma
- bone fracture
- cancer confirmed by histology
- cardiac disease
- CFRD
- chronic *P aeruginosa* colonisation
- chronic *Staphylococcus aureus* colonisation
- cirrhosis with portal hypertension
- cirrhosis with no portal hypertension
- depression
- DIOS
- fibrosing colonopathy/colonic stricture
- gallbladder disease requiring surgery
- gastroesophageal reflux disease (GERD)
- gastrointestinal (GI) bleed (non-variceal) requiring hospitalisation
- GI bleed (variceal) requiring hospitalisation
- Haemoptysis
- Hearing loss
- hypertension
- kidney stones
- liver disease, non-cirrhosis
- liver enzymes elevated
- nasal polyps requiring surgery
- nontuberculous mycobacteria (NTM) infection (not requiring treatment)
- NTM infection (requiring treatment)
- osteopenia
- osteoporosis
- pancreatitis
- peptic ulcer disease
- pneumothorax requiring chest tube
- port inserted or replaced
- rectal prolapse
- renal failure requiring dialysis
- septicaemia
- sinus disease
- other, specify including cataract

Pulmonary exacerbations will be defined by evidence of a CF care episode or hospitalisation with reason pulmonary exacerbation. Respiratory microbiology will include patients with a bacterial culture and evidence of chronic colonisation with *Staphylococcus aureus*, chronic *P aeruginosa*, intermittent *P aeruginosa*, *Burkholderia*, methicillin-resistant *Staphylococcus aureus*, and *Haemophilus influenzae*.

Serious safety outcomes will be defined by combining death, organ transplantations, hospitalisations, and selected CF complications.

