9.3.4.1 Safety (Objective 1)

Safety outcomes for the Ivacaftor Cohort and the Comparator Cohort will include 6 main categories: death, organ transplantation, hospitalisations, CF complications, and pulmonary exacerbations and respiratory microbiology, and serious safety outcomes (composite outcome). The safety outcomes will be analysed for the Historical Cohort.

1. Death: Frequency of death will be calculated and will include cause of death and age at death. Analyses will be stratified by duration of ivacaftor exposure, age, sex, *CFTR* genotype class, percent predicted FEV₁, and comorbid conditions.
2. Organ transplantations: Frequency of organ transplantations will be calculated and will include type of organ transplanted and age at transplant. Analyses will be stratified by duration of ivacaftor exposure, age, sex, *CFTR* genotype class, percent predicted FEV₁, and comorbid conditions.

3. Hospitalisations: Frequency of hospitalisations will be calculated and will include the number of days of hospitalisation, and age at hospitalisation. Analyses will be stratified by duration of ivacaftor exposure, age, sex, *CFTR* genotype class, percent predicted FEV₁, and comorbid conditions.
4. CF complications: Frequency of CF complications will be calculated. CF complications include infections, arthritis, asthma, bone fracture, diabetes, and several hepatic, gastrointestinal, and pulmonary complications. Analyses will be stratified by duration of ivacaftor exposure, age, sex, *CFTR* genotype class, percent predicted FEV₁, and comorbid conditions.
5. Pulmonary exacerbations and respiratory microbiology: Frequencies of pulmonary exacerbations and respiratory microorganisms will be calculated. Analyses will be stratified by duration of ivacaftor exposure, age, sex, *CFTR* genotype class, percent predicted FEV₁, and comorbid conditions.
6. Serious safety outcomes: Frequency of serious safety outcomes will be calculated. Analyses will be stratified by duration of ivacaftor exposure, age, sex, *CFTR* genotype class, percent predicted FEV₁, and comorbid conditions.

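### The ascertainment-bias check in 9.9 uses hospitalisations, a safety endpoint, as one of its two named indicators; that component cannot tell a treatment effect from unequal follow-up

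*Protocol*

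**What the plan says.** Protocol 9.9, under the limitations of observational studies, names the mechanism: "differential follow-up of the patient cohorts, which can introduce ascertainment bias of outcomes". It offers one mitigation, that "the CF patient registries collect comprehensive data at least annually on all patients enrolled", and one diagnostic: "To identify whether ascertainment bias is introduced into the study, cohorts will be compared for healthcare utilisation including CF care visits and hospitalisations". It gives no threshold, no test and no consequence for that comparison.

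Hospitalisations are a safety endpoint in 9.3.3. Section 9.3.4.1 places them among the main outcomes compared between cohorts: "Safety outcomes for the Ivacaftor Cohort and the Comparator Cohort will include 6 main categories: death, organ transplantation, hospitalisations, CF complications". They are also a component of the serious safety composite in both registries (9.3.1.2 and 9.3.2.2). For the UK, 9.3.1.2 narrows the definition: "Hospitalisations will be defined if there is evidence of a start date for a hospitalisation for a pulmonary exacerbation". For the event behind those admissions, 8.3 states a prior expectation: "Pulmonary exacerbations: similar or lower incidence in the Ivacaftor Cohort than the Comparator Cohort".

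On visit data, the Abstract says that "the CF Trust Patient Registry only includes annual data for each patient". Sections 7.2 and 9.4 and Table 7 describe UK collection as encounter-based.

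**The concern.** A bias diagnostic is useful only if it responds to the bias and not to the treatment. Here one of the two named inputs is itself a result of the study. If ivacaftor lowers or raises admissions, the hospitalisation part of the check moves even when both cohorts are observed equally well. If treated patients are watched more closely but have fewer exacerbations, the two can offset and the check looks clean.

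Two things are at stake in a safety study with an untreated comparator. A real change in admissions, benefit or harm, could be discounted as an artefact of follow-up. Real differences in how often patients are seen, cultured or screened for complications could be missed. The point concerns only the diagnostic in 9.9, not the use of healthcare utilisation as a possible adjustment variable in 9.3.5.

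**Working it through.** The protocol gives no hospitalisation rate and no figure for this check, so there is nothing of its own to reproduce. The argument is one of logic; the arithmetic only shows its scale.

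**1. The two indicators set against the outcomes**

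| Indicator in 9.9 | Also an outcome? | Free of treatment effect? |
|---|---|---|
| Hospitalisations, UK | Yes; exacerbation admissions only (9.3.1.2) | No; 8.3 expects similar or lower incidence of exacerbations |
| Hospitalisations, US | Yes; any admission, with reason recorded (9.3.2.2) | No; exacerbation is one of the recorded reasons |
| CF care visits, UK | Not a listed endpoint, but exacerbations are identified from care episodes or admissions (9.3.1.2) | Only for routine visits; information is limited if data are annual |
| CF care visits, US | Not a listed endpoint, but exacerbations are identified from care episodes (9.3.2.2) | Only for routine visits; 9.9 makes no split |

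**2. A treatment effect alone produces a difference**

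Inputs from the documents: best-case exposed N of 432 (UK) and 1035 (US), from 9.5. Assumptions not in the documents: 1:1 cohorts, as in Table 6; annual share hospitalised in comparators p₁ = 20%, 35% or 50%; true relative risk RR = 0.7, 0.8 or 1.25; identical ascertainment; two-sided 5% comparison.

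With p₂ = p₁·RR, d = |p₁ − p₂| and p̄ = (p₁ + p₂)/2:

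Probability of a difference ≈ Φ[(d − 1.96·√(2p̄(1 − p̄)/n)) / √(p₁(1 − p₁)/n + p₂(1 − p₂)/n)]

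Worked case, UK, p₁ = 0.35, RR = 0.8: p₂ = 0.28, d = 0.07, p̄ = 0.315. The null standard error is 0.0316 and the alternative standard error 0.0315. Then (0.07 − 1.96 × 0.0316)/0.0315 ≈ 0.26, and Φ(0.26) ≈ 0.60.

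| RR | p₁ = 20%: n = 432 / 1035 | p₁ = 35%: n = 432 / 1035 | p₁ = 50%: n = 432 / 1035 |
|---|---|---|---|
| 0.7 | 65% / 95% | 92% / >99% | 99% / >99% |
| 0.8 | 33% / 66% | 60% / 93% | 84% / >99% |
| 1.25 | 42% / 78% | 75% / 98% | 96% / >99% |

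This is the power of the hospitalisation endpoint. It shows how often a true effect alone would look like a utilisation difference.

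**3. Bias and effect can cancel**

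Observed ratio = true RR × ratio of ascertainment (ivacaftor to comparator).

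- True RR 0.75, ascertainment 4/3 as high on ivacaftor: 0.75 × 4/3 = 1.00.
- True RR 1.25, ascertainment 0.8 times as high: 1.25 × 0.8 = 1.00.

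In both cases hospitalisations are equal although ascertainment is not.

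**4. Measures that do not carry the outcome already exist**

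Sections 9.6 and 9.9 report completeness, registry-wide and not by cohort. UK: 89% of living patients with at least an annual encounter, and 95% of those with a pulmonary function measure. US, 2011: 94% with medications data, 91% with complications data, 91% with microbiology data, and 96% of non-transplant patients aged 6 or older with pulmonary function tests. Section 9.9 does not use them for the ascertainment check.

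**The case against.** The strongest reply is that the sentence has been read too narrowly and too mechanically. The list is open and puts care visits, which are not an endpoint, first. No threshold or consequence is written, the study is descriptive, and how the comparison will be read can be left to the statistical analysis plan. This stands in part. A reader might infer that the check rests on hospitalisations alone, that a working drug would set off a bias alarm, and that unequal follow-up could never be recognised. The documents do not support that: visits are named, there is no alarm rule, and visit counts could show unequal follow-up.

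Second, a reader might take the UK visit indicator to be empty because of the remark in the Abstract. That is also too strong. Sections 7.2 and 9.4 and Table 7 call UK collection encounter-based, and with only 89% of living patients having an annual encounter, even presence of a visit could differ by cohort. The US check has more substance: 9.3.2.2 describes quarterly visits as standard of care and about 5 pulmonary function measures per patient-year.

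Third, an admission is a contact at which complications and cultures can be found. If ivacaftor reduces admissions, comparators are observed more often for those outcomes. This stands, and is a reason to show admissions next to the other measures rather than drop them.

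Fourth, other safeguards exist: UK checks of patient notes, the annual 5% US audit, and sensitivity analyses for missing data (9.8 and 9.9). They bear on data quality, but none is stated to be by cohort.

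What survives all four is that the protocol itself, not the analysis plan, chose an outcome as an indicator of bias and gave no way of separating the two readings.

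**Conclusion.** The point holds for the hospitalisation component. It cannot distinguish a treatment effect from differential follow-up, and equality on it does not exclude bias. Care visits mitigate this only in part, because routine and exacerbation-driven visits are not separated and because the protocol's descriptions of UK data (annual only, or encounter-based) do not agree.

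Under identical ascertainment and a true 20–30% reduction, a hospitalisation difference would appear in about 33–99% of cases at the UK size and 66% to over 99% at the US size, over assumed baseline risks of 20–50%. These ranges rest on assumed risks and effects, 1:1 cohorts and best-case N (every eligible patient treated). They are not the false-alarm rate of a written rule, since none is written. This is an inexpensive improvement to the method, not a flaw that invalidates the study.

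**What to change.** In 9.9, base the ascertainment check on measures of observation opportunity that are not outcomes, tabulated by cohort:

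- **UK:** share of patients with an annual encounter, with an FEV1 and with a respiratory culture; completeness of the complications form, if the registry can supply it.
- **US:** routine (non-exacerbation) encounters, pulmonary function tests and cultures per patient-year; completeness of medications, complications and microbiology data.

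Report hospitalisations as an outcome. They may be shown in the same table as a contact at which other outcomes can be detected, with a sentence stating that a cohort difference in them is not read as evidence of ascertainment bias. Reconcile the Abstract's description of UK data as annual only with 7.2, 9.4 and Table 7, so that it is clear which UK visit measures exist.

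Cost: a change of wording and about one extra table per registry, from data largely already collected. The main work is splitting US encounters into routine and exacerbation-related using the care-episode data. Availability of complications-form completeness in the UK is not documented and needs confirming.
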